+ 0.0005510715 x (age in	(observable entity)	
years)²		
+ 0.2876587433 [if male]	Answer is Y in case of presence of	Mandatory
	SNOMED: 248153007 Male (finding)	
+ 0.3455832714 [if current	A= last occurrence of smoker SNOMED: <<	Mandatory
smoker]	77176002 Smoker (finding)	(default = N)
	B = last occurrence of	
	Quit-Smoking (<< 160617001 Stopped smoking)	
	OR Ex-Smoker (<< 8392000 Non-smoker)	
	IF time of A is after B,	

¹² Numbers from Dutch population (baseline characteristics from the SMART study); it is valid for male/female and all ages. The same number can be used across the EU population.

Formulas	SNOMED / LOINC Code (available in PHKG)	Population ¹² value if missing
	THEN value is Y FLSE value is N	
+ 0.0018913154 * systolic blood pressure in mmHg	Take last value in PHKG ; SBP= LOINC: 8480-6	Mandatory
	(average value across a period of time)	
+ 0.3181706587 [if diabetic]	Answer is Y in case of presence of SNOMED: << 73211009 Diabetes mellitus (disorder) (and all children codes)	VAL = 17% * 0.223 (average)
+ 0.2947019539 [if history of coronary artery disease, of acute coronary syndrome, myocardial infarction or coronary revascularization]	 Answer is Y in case of presence of SNOMED: << 53741008 Coronary arteriosclerosis (disorder) (and all children codes) OR SNOMED: << 394659003 Acute coronary syndrome (disorder) (and all children codes) OR SNOMED: << 22298006 Myocardial infarction (disorder) (and all children codes) OR SNOMED: << 415070008 Percutaneous coronary intervention (procedure)>> (and all children codes) OR SNOMED: <<232717009 Coronary artery bypass grafting (procedure) >> (and all children codes) 	Mandatory (default = N)
+ 0.3483178604 [if history of cerebrovascular disease, TIA, brain infarction, amaurosis fugax, retina infarction or carotic surgery]	 Answer is Y in case of presence of SNOMED: << 230690007 Cerebrovascular accident (disorder) (and all children codes) OR SNOMED: << 266257000 Transient ischemic attack (disorder) (and all children codes) OR SNOMED: << 432504007 Cerebral infarction (disorder) (and all children codes) OR SNOMED: << 88032003 Amaurosis fugax (disorder) (and all children codes) OR SNOMED: << 175362007 Carotid and/or cerebral and/or subclavian artery operations (procedure) (and all children codes) 	Mandatory (default = N)

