+ 0.0396752081 * eGFR ² (in mL/min/1.73m ² + 0.0002186126 * eGFR ² (in mL/min/1.73m ²) + 0.1517601731 * log(High	Last value LOINC: 62238-1 If not available, derive from creat(SerumCreatine in micromol/l (LOINC = LP145994-2) (per paper Based on Heart. 2013 Jun;99(12):866-72 & Circulation. 2016 Nov 8;134(19):1419-1429 eGFR in mL/min per 1.73 m2 = If patient is male (SNOMED: 248153007) THEN = 32788 * creat ^(-1.154) * age ^(-0.203) ELSE 32788 * creat ^(-1.154) * age ^(-0.203) * 0.742 If the last value of LOINC: 30522-7 is above 15 then	VAL creatine = 92 micromol/l (to be transformed) VAL = 2.2mg/l =
Sensitivity-CRP in mg/dL)	use the previous value (up to the time the value is below 15). If there is no value below 15, then take default	22mg/dL

Formulas	SNOMED / LOINC Code (available in PHKG)	Population ¹² value if missing
+ 0.2107210313 * usingAnticoag	 Answer is Y in case of presence of one or more drugs of category Platelet aggregation inhibitors excl. Heparin (ATC = B01AC) OR A combination of One or more drugs of category Platelet aggregation inhibitors excl. Heparin (ATC = B01AC) + one or more drug of category Direct factor Xa inhibitors (ATC = B01AF) 	VAL = Y
	 Example: can be Ascal, aspirin or an other equivalent (AAS, carbasalate calcium) Dual antiplatelet therapy : Ascal / aspirin + a P2Y12 inhibitor Direct oral anticoagulants (DOAC) P2Y12 inhibitor Ascal / Aspirin + low dose direct working oral anticoagulation (DOAC) 	

In case of missing data, some parameters can use population average value as indicated in the last column. If a mandatory value is missing, the default value indicated in the last column will be used. Note: it is expected that birthdate, gender and systolic blood pressure will be available. The score will be computed by AIDAVA and by the treating (junior) physician. It will then be checked by the senior physician; in case of discrepancy between the score computed by AIDAVA and by the physicians, the senior physician will require explanations on how AIDAVA came to the different answers/codes needed to compute the score and decide the reason for discrepancy.

The senior physicians will be presented with a table with all the parameters used to compute the score (as displayed in the figure below) and be able to get information on how AIDAVA came to a certain value (which data source, which transformation).

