- Alternative hypothesis (H2 CVD): AIDAVA G1 provides an accurate SMART score (accuracy of 80%+) on patients, across sites, without any time spent by CVD specialists. G2 has similar or better results.

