10.6. SMART risk score

#Last update: 27 - 01 - 2022

smart2 <- function(age, sex, isSmoking, sbp, diabetesDiagnosis, coronaryArteryDisease, cerebrovascularDisease, peripheralArteryDisease, aorticAneurysm, yearsSinceFirstDiagnosis, hdlCholesterol, totalCholesterol, creatinin, crp, hrFutureEvent = 1, usingAnticoag, region){

LP <- NULL tenYearRisk <- NULL

sex <- ifelse(sex==1, "M", "F")</pre>

#Berekenen eGFR obv CKDepi
gfr <- ifelse(sex=="M", 32788*creatinin^(-1.154)*age^(-0.203),
32788*creatinin^(-1.154)*age^(-0.203)*0.742)</pre>

#Berekenen non-HDL obv totaal cholesterol en HDL nonHdl <- totalCholesterol - hdlCholesterol

LP= -0.0349602236 * age + 0.0005510715 * age^2 + ifelse(sex=="M", 0.2876587433, 0) + 0.3455832714 * isSmoking + 0.0018913154 * sbp + 0.3181706587 * diabetesDiagnosis + 0.2947019539 * coronaryArteryDisease + 0.3483178604 * cerebrovascularDisease + 0.3303566308 * aorticAneurysm +

¹⁸ As defined in European Risk Regions (heartscore.org) -Netherland: Low; Austria: moderate; Estonia: High

0.2244665798 * peripheralArteryDisease + 0.0476995851 * yearsSinceFirstDiagnosis -0.0016497342 * yearsSinceFirstDiagnosis^2 + 0.5403642493 * log(nonHdl) -0.0396752081 * gfr + 0.0002186126 * gfr^2 + 0.1517601731 * log(crp) -0.2107210313 * usingAnticoag

tenYearRisk <- 1 - (1-0.1658228)^exp(LP + 0.0463729 - log(ratioRegion)) tenYearRisk <- ifelse(tenYearRisk==1,0.9999999,tenYearRisk)

tenYearRiskWithTreatment <- 1 - (1-tenYearRisk)^(hrFutureEvent) #hrFutureEvent komt uit behandeleffectenscript

return(

) }

```
list(
currentTenYearRisk = tenYearRisk,
tenYearRiskWithTreatment = tenYearRiskWithTreatment
)
```

11. Regulatory, Ethical, and Study Oversight Considerations

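### Read literally, the SMART current-smoker rule scores a patient with a smoker entry and no stop or non-smoker entry as a non-smoker

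*Protocol*

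**What the plan says.** The SMART specification in protocol Section 3.2.2 has a row for current smoking with coefficient "0.3455832714 [if current" smoker]. It defines two dated items:

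- A: "A= last occurrence of smoker SNOMED: <<" 77176002.
- B: the last occurrence of "Quit-Smoking (<< 160617001 Stopped smoking") or of the ex-smoker/non-smoker code.

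The decision is "IF time of A is after B", then "THEN value is Y FLSE value is N" (the second keyword is evidently ELSE). The last column marks the row mandatory with default N. The text after the table adds: "If a mandatory value is missing, the default value indicated in the last column will be used".

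The code in Section 10.6 uses the same coefficient, "0.3455832714 * isSmoking", and takes smoking status as an input that has already been derived.

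CVD Metric 2 compares AIDAVA's score with the physician's as a percentage difference. The related hypothesis in Section 9.1 is that "AIDAVA G1 provides an accurate SMART score (accuracy of 80%+) on patients".

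**The concern.** The row is meant to identify current smokers, but the rule can return Y only when there is a B entry for A to be later than. The natural record of someone who smokes and has never stopped has an A and no B. That is the central case for the row, and the rule has no branch for it.

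If the case resolves to N, AIDAVA drops the smoking term while the physician, who knows the patient smokes, includes it. The two scores then differ because of the specification, not because of how well the record was curated. The error has one direction (AIDAVA too low), and it enters a secondary endpoint that is meant to measure AIDAVA's performance.

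**Working it through.** **Step 1: run the rule on each type of record.**

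| Record | Is A after B? | Result | Intended |
|---|---|---|---|
| Stopped, then smoker | yes | Y | Y |
| Smoker, then stopped | no | N | N |
| Smoker only, no B | cannot be met | N by the ELSE branch | Y |

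If the absent B were instead treated as a missing mandatory value, the default is N as well. Section 10.6 does not help, because smoking status arrives there already set. No text in the protocol returns Y for the third record.

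**Step 2: compare with neighbouring rows of the same table.** Total and HDL cholesterol have a substitute when the value is not available. CRP has a default when no usable value exists. Diabetes and the disease-history rows test simple presence. The smoking row is a yes/no item that depends on comparing two dates, and it says nothing on what happens when one date does not exist.

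**Step 3: size under the Section 10.6 form.** The plan gives no figure for this, so there is none to reproduce. In 10.6, risk = 1 - S^exp(LP + constant). Removing the smoking coefficient b = 0.3455832714 from LP multiplies the exponent by exp(-b) = 0.7078. With r the risk scored correctly as a smoker and r0 the risk scored as a non-smoker:

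r0 = 1 - (1 - r)^0.7078, and relative shortfall = 1 - r0/r.

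This does not depend on the baseline S, the recalibration constant or the regional ratio.

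| r | r0 | Shortfall |
|---|---|---|
| 10% | 7.2% | 28% |
| 20% | 14.6% | 27% |
| 30% | 22.3% | 26% |
| 40% | 30.3% | 24% |
| 50% | 38.8% | 22% |
| 80% | 68.0% | 15% |

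The shortfall cannot exceed 1 - 0.7078 = 29%. It falls to 20% at a true risk of about 62%.

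As a cross-check, the full 10.6 function was run for an assumed male patient: systolic pressure 140, coronary disease only, one year since diagnosis, total cholesterol 4.9, HDL 1.2, creatinine 92, CRP 2.2, antithrombotic Y, regional ratio 1. The score drops from 13.2% to 9.6% at age 50, 17.0% to 12.3% at 60, 23.9% to 17.6% at 70 and 36.0% to 27.1% at 80, so it is 25-28% too low.

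**Step 4: size under the 3.2.2 formula.** Section 3.2.2 prints different constants (0.71840 and +1.933). Take a patient whose 10.6 score is 17.2% at regional ratio 1.

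- Linear predictor: ln(0.828)/ln(0.8341772) = 1.041; ln(1.041) - 0.0464 = -0.006.
- Under 10.6, without smoking: 1 - 0.828^0.7078 = 12.5%, a shortfall of 27%.
- Under 3.2.2, reading the exp term as an exponent and keeping the same linear predictor: 1 - 0.71840^exp(1.927) = 89.7%. Without smoking: 1 - 0.71840^exp(1.581) = 80.0%. The shortfall is (89.7 - 80.0)/89.7 = 11%.

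The direction is the same under both, but the size is not.

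**The case against.** The strongest reply is that N is an inference. The row is clinician-level pseudo-code, spread over a page break, with no rule for absent entries. A programmer could sensibly treat an absent B as never having stopped and return Y, which fits the row's label. It can also be argued that the default never applies, since a record with a smoker entry is not missing its smoking status. Both points stand. N is the literal reading, not a proven behaviour of the software. The gap still needs closing, because Section 2.2 wants the same extract and the same algorithm at every site and the result should not depend on how absent values are handled.

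A reader might infer more than the documents support:

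- **That each affected patient breaks the 80% target.** The target is not defined, and Section 9.1 states it across patients. If it means within 20% of the physician for each patient, an affected patient with true risk below about 62% fails under the 10.6 code. If it means average error, and this were the only error, even a 28% shortfall would need 0.20/0.28 = 71% of patients, or 33 of 45. If it means the share scored correctly, 10 of 45 would be needed (35/45 = 78%).
- **A count of affected patients.** The protocol gives neither smoking prevalence nor recording practice, so any number is assumption.
- **That the error persists unchanged into G2.** The protocol foresees software testing, senior physicians see each parameter and its source, and G2 is an improved version. The fault could be noticed and corrected.
- **That same-date entries must resolve to Y.** CVD patients may be enrolled during the index infarction, so a smoker and a stopped entry on one day may describe someone who has just quit. The choice is open.

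Senior review does not remove the problem. It follows the scoring, and its three reasons are an incomplete record, an AIDAVA error or a physician error. A fault in the rule itself has no category and would probably be logged as an AIDAVA error.

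**Conclusion.** The point holds for the rule as written. For a record with a smoker entry and no stop or non-smoker entry, the literal result is N and no other text gives Y. Where N is applied, the 10.6 code under-scores by about 24-28% at true risks of 10-40%; this follows from the protocol's own coefficient and needs no assumption about baseline or region. Under the 3.2.2 constants the one profile examined gives about 11%, so the size is conditional on which formula is used. What is established is a specification-made, one-directional disagreement with the physician in CVD Metric 2. Its frequency, and its effect on whether the 80% hypothesis is met, cannot be derived from the protocol.

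**What to change.** In the current-smoker row of Section 3.2.2, state: value is Y if A exists and either B does not exist or A is later than B; value is N otherwise. The sponsor should also state how entries with the same date are resolved.

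Before use, run the rule on three records: smoker entry only (expect Y), smoker then stopped (expect N), stopped then smoker (expect Y).

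Reconcile the formula constants in 3.2.2 with those in 10.6, so that AIDAVA's score has a single definition.

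The smoking clause costs one line in the specification and its implementation, and needs no new data. The reconciliation is a separate check of the two sections against each other.

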+ 0.3303566308 [if abdominal aortic aneurysm, history or presence of supra- or infrarenal aneurysm of the aorta > 3 cm, or aortic surgery]	 Answer is Y in case of presence of SNOMED: << 233985008 Abdominal aortic aneurysm (disorder) (and all children codes) OR SNOMED: << 67362008 Aortic aneurysm (disorder) (and all children codes) OR SNOMED: << 32907006 Operation on aorta (procedure) (and all children codes) 	Mandatory (default = N)
+ 0.2244665798 [if peripheral artery disease, history or presence of claudicatio intermittens, lowered ankle-arm index or surgical intervention (like angioplasty,	 Answer is Y in case of presence of SNOMED: << 840580004 Peripheral arterial disease (disorder) (and all children codes) OR SNOMED: << 63491006 Intermittent claudication (finding) (and all children codes) OR SNOMED: << 446841001 Ankle brachial 	Mandatory (default = N)

Formulas	SNOMED / LOINC Code (available in PHKG)	Population ¹² value if missing
stenting, endarterectomy, vascular bypass or amputation)]	 pressure index (observable entity) (and all children codes) OR SNOMED: << 387713003 Surgical procedure (procedure) (like <418285008 Angioplasty of blood vessel (procedure)> OR <233434005 Insertion of stent into vein (procedure)> OR <392031002 Endarterectomy (procedure)> OR <116360008 Arterial bypass graft (procedure)> (and all children codes) 	
 + 0.0476995851 x years since first diagnosis of vascular disease + 0.0016497342 x years since first diagnosis of vascular disease A2 	 years (YRS) = current year - Y1 (year of first diagnosis of any of the above 4 diagnosis groups) Y1 = smallest of A,B,C,D where A = year of first occurrence of coronary artery disease B = year of first occurrence of history of cerebrovascular disease C = year of first occurrence of abdominal aortic aneurysm D = year of first occurrence of peripheral artery disease years = YRS as above 	VAL= 1 year
+ 0.5403642493 x log(nonHDL)	 nonHDL = total-cholesterol - HDL-cholesterol WHERE total-cholesterol in mmol/L = Last value LOINC: 14647-2 OR if not available VAL = 4.9 mmol/l HDL-cholesterol in mmol/L = Last value LOINC : 14646-4 OR if not available VAL = 1.2 mmol/l 	For all lab value, if the unit of measurement is different in the ontology that the one in the formula transform with unit needed

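### Two SMART history rules do not match the definitions beside them: the aortic rule also admits non-abdominal aneurysms, and the cerebrovascular codes neither name retinal infarction nor stop at carotid surgery

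*Protocol*

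**What the plan says.** The technical table in Protocol section 3.2.2 pairs a definition and coefficient with a list of codes for each history item.

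- **Aortic item, definition:** "0.3303566308 [if abdominal aortic aneurysm, history or presence of supra- or infrarenal aneurysm of the aorta > 3 cm, or aortic surgery".
- **Aortic item, rule:** yes if the record holds the abdominal aneurysm code 233985008, or "SNOMED: << 67362008 Aortic aneurysm (disorder) (and all children codes", or the code for an operation on the aorta.
- **Cerebrovascular item, definition:** "0.3483178604 [if history of cerebrovascular disease, TIA, brain infarction, amaurosis fugax, retina infarction or carotic surgery".
- **Cerebrovascular item, rule:** yes for cerebrovascular accident, TIA, cerebral infarction, "SNOMED: << 88032003 Amaurosis fugax (disorder) (and all children codes", or "175362007 Carotid and/or cerebral and/or subclavian artery operations (procedure".

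Both rows default to no when no code is found. The coefficients agree with the R function in section 10.6: "0.3483178604 * cerebrovascularDisease + 0.3303566308 * aorticAneurysm".

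Cardiovascular Metric 2 (section 3.2.2) is the percentage difference between AIDAVA's score and the physician's. Section 9.1 sets an accuracy target of 80% or more. For each discrepancy the senior physician chooses one of three reasons: an incomplete record, an error in AIDAVA, or an error by the physician.

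**The concern.** Metric 2 is meant to show whether AIDAVA curates the record well enough to reproduce the clinician's score. That works only if both sides score the same item. If the physician applies the written definition and AIDAVA applies a code list that is wider in one row and apparently narrower in another, the two can differ on a perfectly curated record. The difference then comes from the specification, not from curation. Since none of the three reasons covers a specification fault, such a case would most naturally be booked as an AIDAVA error. The accuracy endpoint would be biased against the tool, and the explanation of discrepancies would be misleading.

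**Working it through.** **1. Definition against rule**

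| Item | Definition | Code rule | Mismatch |
|---|---|---|---|
| Aortic | Abdominal aneurysm; supra- or infrarenal aneurysm > 3 cm; aortic surgery | Abdominal code, general aortic aneurysm code with all children, aortic operation code | No site condition on the general code, so a non-abdominal aneurysm scores yes |
| Cerebrovascular, diagnoses | Includes retinal infarction | Four diagnosis codes; the only eye-related one is amaurosis fugax | No code named for retinal infarction |
| Cerebrovascular, surgery | Carotid only | One code for carotid, cerebral or subclavian operations | Cerebral and subclavian operations also score yes |

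In the same table, line C of the years-since-diagnosis rule calls the aortic group abdominal aortic aneurysm. This supports the abdominal site as the intended one.

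**2. Size of one wrongly set item, section 10.6 code**

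The protocol states no figure to reproduce. The function is

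risk = 1 − (1 − 0.1658228)^exp(LP + 0.0463729 − log(ratioRegion)).

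Wrongly adding coefficient b turns a true risk r into 1 − (1 − r)^exp(b). Wrongly omitting it gives 1 − (1 − r)^exp(−b).

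- False aneurysm: exp(0.3303566) = 1.391.
- Missed cerebrovascular item: exp(−0.3483179) = 0.706.

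| True risk | False aneurysm | Missed cerebrovascular |
|---|---|---|
| 10% | 13.6% (+36%) | 7.2% (−28%) |
| 20% | 26.7% (+33%) | 14.6% (−27%) |
| 30% | 39.1% (+30%) | 22.3% (−26%) |
| 50% | 61.9% (+24%) | 38.7% (−23%) |

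Worked example (assumed: man aged 65, non-smoker, no diabetes, systolic pressure 135, coronary item yes, 0 years since diagnosis, antithrombotic item yes, default laboratory values of section 3.2.2, ratio 1). LP = −0.244 and risk = 1 − 0.8341772^exp(−0.1976) = 13.8%. A false aneurysm gives 18.7%, which is +35%. With a true cerebrovascular item the risk is 19.0%; missing it returns 13.8%, which is −27%.

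For men and women aged 50 to 80 on the same inputs, with ratios 0.7, 1.0 and 1.3 (assumed, as the values are not in the text shown), the ranges are +29% to +37% and −23% to −28%.

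**3. Same patients, formula printed in section 3.2.2**

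That formula is 1 − 0.71840^exp(A + 1.933). With the same linear predictor (signs as in 10.6), the man aged 65 has a risk of 83.3%. A false aneurysm gives 91.7% (+10%); a missed cerebrovascular item gives 83.3% instead of 92.1% (−10%). Over ages 50 to 80 and both sexes, the ranges are +2% to +18% and −2% to −16%. Baseline risks are already near the ceiling, so relative changes are small.

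**4. Effect on the whole group**

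The documents give no prevalence. If 1% to 3% of patients were affected (an assumption), that is 45 × 0.01 = 0.45 to 45 × 0.03 = 1.35 patients. At an error of 35%, the mean absolute percentage difference would move by 0.01 × 35 = 0.35 to 0.03 × 35 = 1.05 points.

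**The case against.** The strongest reply is that these cases are rare and will be seen. The senior physician reviews discrepancies parameter by parameter, with data source and transformation shown, and a shift of about one point in the group mean is unlikely to change the conclusion. This stands as to size. It does not cure the labelling, because the right reason is not among the three choices.

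Four stronger readings are tempting, and the documents do not support them:

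- **That small abdominal aneurysms are wrongly counted.** The definition is a comma-separated list. If abdominal aortic aneurysm stands alone as a criterion, the 3 cm limit applies only to the entry after it. The site mismatch holds on either reading; the size mismatch does not.
- **That a non-abdominal aneurysm certainly back-dates the years since first diagnosis.** Line C says abdominal, so on its literal wording that year does not enter. The adjacent reference to the diagnosis groups above allows the opposite reading. The point is unclear.
- **That each error by itself breaches the 80% target.** Section 9.1 does not say whether accuracy means per-patient relative error, a mean, or the share of patients who agree. A 20% per-patient allowance is one interpretation. Under the section 3.2.2 formula none of the errors computed reaches 20%.
- **That retinal infarction is definitely missed.** No listed code is named for it, but whether it is a child of one that is listed cannot be checked from the documents.

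Two further limits stand. The item wording in the web calculator is not in the documents, so it is an assumption that the physician follows the written definition. A score also changes only if no other code in the same row already makes the item positive. Cerebral artery operations could be argued to fall under cerebrovascular disease in general; subclavian operations are the clearer excess.

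**Conclusion.** The mismatch is real but minor. On the text alone, the aortic rule is wider than its definition as to site, the operation code is wider than carotid surgery, and retinal infarction is defined but not named in the codes. Under the section 10.6 function a wrongly set item moves that patient's score by about +29% to +37% or −23% to −28%, given the assumed profiles and regional ratios; under the section 3.2.2 formula by about 2% to 18%. Those two formulas conflict and need separate reconciliation, so neither range can be taken as final. Few of the 45 patients are likely to be affected. The main consequence is misattribution: a correctly curated record can be counted against AIDAVA because of the specification. The point is worth correcting mainly because correction is cheap.

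**What to change.** Reconcile the code lists with the written definitions before the score is run, with the clinical leads confirming which wording governs.

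- **Aortic row.** Limit the rule to the abdominal site. Alternatively, keep 67362008 but exclude its child codes that specify a non-abdominal site, so that records with no site given still count. State whether a size condition applies, and to which entries. Use the same group for line C of the years-since-diagnosis rule.
- **Cerebrovascular row.** Check in the terminology whether a listed code already captures retinal infarction, and add its code if none does. Limit the operation code to the procedures in the definition.

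The cost is an edit to two rows and one terminology check; no new data are collected. There is one small downside: if 67362008 is dropped entirely, aneurysms coded without a site are no longer counted automatically. The exclusion variant avoids this.

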3.2.2 Cardiovascular Use case

Objective. The objective of the endpoints below is to demonstrate the value of having interoperable and reusable data in a standard format to generate valuable and high-quality information in clinical care, without additional burden to the treating physicians.

Objective	(Secondary) end point
Metric 1. Compare scoring time	Metric definition: Time to compute the SMART score (see
between AIDAVA and CVD	definition below)
expert	
	Measurement:

Objective	(Secondary) end point	
	TCVD. Time required for the treating physician to compute the SMART risk score (collect + analyse + enter data into a standalone web page calculator) - per estimate of user in dedicated entry form - compared to the time needed to calculate the same score by AIDAVA, automatically (G1 and G2)	
Metric 2: Compare scoring accuracy between AIDAVA and CVD expert	Metric definition: Accuracy of automatic calculation of the U-Prevent SMART risk score compared to cardiovascular expert-entered score calculation (% difference in the score output - per estimate of user in dedicated entry form) (G1 and G2)	
	 Measurement: CVD1. U-Prevent SMART score computed by treating physician (https://u-prevent.com/calculators/smartScore) CVD2. U-Prevent SMART score computed by AIDAVA 	

The SMART Risk Score [4] is a tool to estimate 10-year risk for recurrent vascular events in patients with manifest cardiovascular disease. The calculator is located at the U-Prevent site [5], a clinical decision support platform, for the application of risk prediction models in clinical practice; the calculator has been recreated and optimised by ORTEC for personalised cardiovascular risk management. The U-Prevent site is CE marked according to the Medical Devices Directives (MDD); marking for MDR compliance is in progress. The pilot site was built by UMC Utrecht. Using the calculators is free. The U-Prevent team develops extra services for premium users, optimization of data management, e.g. by FAIR and GDPR-compliant data exchange from electronic health records. Technical specification to compute Model A, the SMART Risk Score [6] can be found below.

Formulas	SNOMED / LOINC Code (available in PHKG)	Population ¹² value if missing
Recalibrated SMART risk score for	patients with CVD:	
10-year cardiovascular disease risk	: (%) = (1- 0.71840 exp[A + 1.933]) x 100%	
where A =		
-0.0349602236 x age in years	Compute from SNOMED: 184099003 Date of birth	Mandatory

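### The SMART score specification in section 3.2.2 contradicts the code in section 10.6 (three signs, the baseline, a regional ratio); taken as printed, it returns about 100%

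*Protocol*

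**What the plan says.** Section 3.2.2 introduces its table as the technical specification for the SMART risk score. The risk equation is printed as "1- 0.71840 exp[A + 1.933]) x 100"%, where A is a sum of coefficient terms. In that sum a plus precedes each of "0.0396752081 * eGFR", "0.0016497342 x years since first diagnosis of vascular disease" (the squared term) and "0.2107210313 * usingAnticoag".

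Section 10.6 prints R code for the score with the same coefficients to ten decimals. There the years terms are "0.0476995851 * yearsSinceFirstDiagnosis -0.0016497342 * yearsSinceFirstDiagnosis^2". The later terms, with a minus before the first, read "0.0396752081 * gfr + 0.0002186126 * gfr^2 + 0.1517601731 * log(crp) -0.2107210313 * usingAnticoag". The risk line is "tenYearRisk <- 1 - (1-0.1658228)^exp(LP + 0.0463729 - log(ratioRegion", and a footnote places the Netherlands, Austria and Estonia in the low, moderate and high risk regions.

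Section 3.2.2 also sets input rules. A missing CRP, or one with no value below 15, takes a default stated as 2.2 mg/l and equated with 22 mg/dL. Peripheral artery disease is defined with a lowered ankle-arm index or a surgical intervention. Its code list, however, accepts the presence of an ankle brachial pressure index and includes "387713003 Surgical procedure (procedure") with vascular operations given as examples.

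CVD Metric 2 is the percentage difference between AIDAVA's score and the score the physician obtains from the U-Prevent web calculator. Section 9.1 (H2-CVD) expects an accuracy of 80% or more.

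**The concern.** Identical coefficients show that the two sections describe one model, so opposite signs and different baselines cannot both be right. Metric 2 is meant to show whether AIDAVA can assemble the right inputs from heterogeneous records. If the formula itself is wrong, the disagreement with the physician's calculator says nothing about those inputs.

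A score held at its ceiling also cannot show change in modifiable risk factors between G1 and G2, which is the stated aim of calculating it at both. The three reasons for discrepancy offered to the senior physician (incomplete record, AIDAVA mishandling recorded information, physician error) do not include a wrong formula. A specification error would therefore be filed under one of the others.

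**Working it through.** The protocol gives no worked risk to reproduce, so both equations were evaluated as printed.

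**Inputs.** The coefficients and baselines come from 3.2.2 and 10.6. The patient is assumed: man, 65, non-smoker, not diabetic, systolic pressure 135, coronary disease only, 1 year since diagnosis, non-HDL 3.7 (the protocol's defaults, 4.9 − 1.2), eGFR 80, CRP 2.2, on antithrombotic treatment. The regional ratio has no visible value; 1 is assumed and 0.5 to 2 shown.

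**Terms on which the sections agree.** Age −2.2724, age squared +2.3283, male +0.2877, systolic pressure +0.2553, coronary disease +0.2947, years +0.0477, 0.5403642493 × ln 3.7 = +0.7070, 0.0002186126 × 80² = +1.3991, 0.1517601731 × ln 2.2 = +0.1197. Sum: 3.1670 before rounding.

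**Terms with opposite signs.** eGFR 0.0396752081 × 80 = 3.1740; years squared 0.0016; antithrombotic 0.2107. Sum: 3.3864.

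- 10.6: LP = 3.1670 − 3.3864 = −0.2194
- 3.2.2: A = 3.1670 + 3.3864 = 6.5534

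**Risk = 1 − exp(−H)**, with −ln 0.8341772 = 0.18131 and −ln 0.71840 = 0.33073.

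| Signs | Baseline | H | Risk |
|---|---|---|---|
| 10.6 | 10.6, ratio 1 | 0.18131 × exp(−0.2194 + 0.0464) = 0.1525 | 14.1% |
| 10.6 | 10.6, ratio 0.5 | 0.3050 | 26.3% |
| 10.6 | 10.6, ratio 2 | 0.0763 | 7.3% |
| 10.6 | 3.2.2 | 0.33073 × exp(−0.2194 + 1.933) = 1.835 | 84.0% |
| 3.2.2 | 10.6, ratio 1 | 0.18131 × exp(6.5534 + 0.0464) = 133 | 100.0% |
| 3.2.2 | 3.2.2 | 0.33073 × exp(6.5534 + 1.933) = 1,603 | 100.0% |

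The baselines alone differ by a hazard factor of (0.33073 × e^1.933) / (0.18131 × e^0.0463729) = 12.0 at ratio 1. Changing one sign at a time on the 10.6 baseline gives 100.0% for eGFR, 20.7% for the antithrombotic term and 14.2% for years squared (small at 1 year, but it grows with the square of time). The eGFR sign therefore drives the result.

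The printed text attaches a square to the first eGFR term, possibly a text-conversion fault. It was read as linear; squared, it would add 253.9 instead of 3.17. In 200,000 simulated coronary patients (ages 35 to 90, eGFR about 14 to 150), the lowest risk from 3.2.2 as printed was 99.98%.

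**CRP default.** 2.2 mg/l ÷ 10 = 0.22 mg/dL, so the printed 22 is 100 times too high on the mg/dL scale that 3.2.2 names. The hazard factor is exp(0.1517601731 × ln 100) = 2.01. If the term in fact takes mg/L and 22 is entered, the error is tenfold and the factor is exp(0.1517601731 × ln 10) = 1.42. The profile above enters 2.2, the mg/L scale; with 0.22, 10.6 gives 10.2% and 3.2.2 still gives 100.0%.

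**Peripheral artery rule.** A false flag multiplies the hazard by exp(0.2244665798) = 1.25, which moves the 14.1% to 17.4%.

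**The case against.** *The signs could be PDF damage.* This is unlikely. The minus on the age term survives in the same table, and the minus signs survive in 10.6. If the offset were really −1.933, the profile would still give H = 0.33073 × exp(6.5534 − 1.933) = 33.6, that is 100.0%.

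*The error would be caught.* The protocol annexes the code, requires software testing, and has the senior physician review discrepancies. Scores stuck at 100% would be noticed. This stands as a limit on the consequence: it depends on literal implementation of 3.2.2. It does not correct the text, and no step requires the two formulas to agree.

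*The stakes are modest.* The score is a secondary endpoint of a prototype barred from clinical decisions, and the primary metrics do not use it. That is correct.

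Some stronger readings are tempting, but the documents do not support them:

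- That the CRP default conflicts with 10.6. The code shows neither a CRP default nor a unit; the slip lies within 3.2.2 and applies only when CRP is missing or never below 15.
- That defaulting missing coronary disease to No is an error because every CVD patient has a confirmed infarction. The default acts only when AIDAVA has not captured the infarction. That is a failure the metric should detect, and defaulting to Yes would hide it.
- That any surgical code certainly triggers the peripheral artery flag. The bracketed vascular examples can be read as limiting it; the limit is merely unclear.
- That a single input error breaches a 20% limit. The 80% accuracy target is not defined as a per-patient relative error.

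**Conclusion.** The contradiction between 3.2.2 and 10.6 is plain on the page and must be reconciled. On the assumed profile it is the difference between 14.1% (7.3% to 26.3% over the assumed ratios) and 100.0%; the baseline alone accounts for a move to 84.0%. The size rests on assumed patient values and an assumed regional ratio, but the ceiling result does not depend on the CRP scale, the regional ratio or the reading of the eGFR term.

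A reader might infer that 10.6 is correct and that H2-CVD is bound to fail. The documents do not go so far. They do not show which equation the web calculator runs, and the failure follows only if 3.2.2 is coded as printed. In that case AIDAVA could not agree with any physician score resembling 10.6, and CVD Metric 2 would be uninformative about curation. The CRP conversion is a definite but secondary error. The acceptance of any ankle brachial index contradicts the table's own definition, and the surgical code needs a stated limit.

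**What to change.** Replace the two formulas with one versioned specification, confirmed against the calculator the physicians will use. It should fix the signs, the baseline, the regional ratio for each country and the CRP unit. Correct the CRP conversion. Align the peripheral artery codes with the table's definition: a lowered index, and procedures limited to peripheral arteries. Leave the coronary disease default as it is. Before each generation is released, run a small set of test inputs through AIDAVA and the calculator and require identical output.

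The cost is the correction of one table and a short software test. Visits, patients and data collection are unchanged.
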